17.3 Primary endpoint

The primary endpoint is change from baseline (randomisation) to end of main trial period (Week 34) in truncal fat percentage.

The primary objective of the trial is to demonstrate the efficacy of once weekly dosing of NNC0195-0092 after 34 weeks of treatment in adults with GHD and the primary analysis of the primary endpoint will be the primary tool for achieving this. Body composition is measured by DXA and truncal fat percentage is defined as 100 times truncal fat mass (kg) divided by the sum of truncal fat mass (kg) and truncal lean body mass (kg).

Truncal fat percentage as a function of time since baseline is expected to be monotone if the subject stays on the randomised treatment in the main trial period. Based on this assumption, the primary analysis of the primary endpoint will be conducted using a multiple imputation technique where the trajectory after a withdrawn subject’s last observation is imputed based on data from the placebo arm, thus mimicking an intention to treat (ITT) scenario where withdrawn subjects are assumed to be switched to no treatment (placebo) after withdrawal. For each of 100 copies of the dataset (seed=34247), an analysis of covariance (ANCOVA) model with GHD onset type (adult or child), sex, region, DM (diabetic status) and sex by region by DM interaction as factors and baseline truncal fat (%) as a covariate. is fitted to the change in truncal fat percentage from baseline to 34 weeks data for the placebo group only. The estimated parameters, and their variances, from this model are used to impute missing values at 34 weeks for subjects in all treatment groups, based on

their sex, region, DM, GHD onset type and baseline truncal fat values. If a truncal fat assessment for a subject has been performed after baseline at intermediate time t (e.g. in connection with the end-of-trial visit for withdrawn subjects, section 8.2) this information will be combined with the time-normalized model based estimate so that the final imputed value for the subject is a sum of the observed value at time t and the model based estimated change multiplied by (34 weeks-t)/(34 weeks) minus the baseline value.

For each of the complete data sets, the change from baseline to 34 weeks is analysed using an ANCOVA model with treatment, GHD onset type, sex, region, DM and sex by region by DM interaction as factors and the baseline truncal fat value as a covariate.

The estimates and standard deviations for the 100 data sets are pooled to one estimate and associated standard deviation for each treatment comparison using Rubin's formula:

$$m_{MI} = \frac{1}{100} \sum_{i=1}^{100} m_i, \quad SD_{MI} = \sqrt{\frac{1}{100} \sum_{i=1}^{100} SD_i^2 + \left(1 + \frac{1}{100}\right) \left(\frac{1}{100-1}\right) \sum_{i=1}^{100} (m_i - m_{MI})^2},$$

where m_i and SD_i are the estimated means and standard deviations for the 100 copies of the dataset, and m_{MI} , SD_{MI} are the pooled estimates.

From m_{MI} and SD_{MI} , the treatment difference at Week 34 between NNC0195-0092 and placebo will be estimated and the corresponding 95% CI and p-value will be calculated. As a secondary comparison, the treatment difference at Week 34 between NNC0195-0092 and Norditropin[®] FlexPro[®] will be estimated and the corresponding 95% CI will be calculated.

Superiority of NNC0195-0092 over placebo will be considered confirmed if the upper boundary of the two-sided 95% CI of the treatment difference (NNC0195-0092 – placebo) is below 0 (i.e. greater reduction from baseline in truncal fat percentage in the NNC0195-0092 treated group than in the placebo treated group).

The secondary comparison, comparison of NNC0195-0092 with Norditropin[®] FlexPro[®], will be used to assist the clinical judgment of the clinical relevance of the estimated treatment difference between NNC0195-0092 and placebo.

A secondary analysis of the primary endpoint based on an assumption of missing at random (MAR) will be done using an ANCOVA model with treatment (i.e. NNC0195-0092, placebo and once-daily Norditropin[®] FlexPro[®]), GHD onset type (adult or child), sex, region, DM and sex by region by DM interaction as factors and baseline truncal fat (%) as a covariate. From the model the treatment difference at Week 34 between NNC0195-0092 and placebo will be estimated and the corresponding 95% CI and p-value will be calculated. Subjects without Week 34 data for the

endpoint will not be included in the analysis. As a secondary comparison, the treatment difference at Week 34 between NNC0195-0092 and Norditropin[®] FlexPro[®] will be estimated from the model and the corresponding 95% CI will be calculated.

An additional supportive analysis of the primary endpoint will be done using the same model as were used for the secondary analysis of the primary endpoint. Only subjects who have completed at least 3 dose adjustment evaluations (see section [5.3.1](#)) and have Week 34 data for the endpoint will be included in this analysis.

The secondary analysis of the primary endpoint is based on the assumption of missing at random (MAR). For this trial the missing data are expected to be mainly due to subjects that are withdrawn from the trial. The possible withdrawal reasons and criteria are described in section [6.6](#). Up to 7% of the subjects are expected to drop-out from the main part of this trial. Data from subjects who withdraw from the trial due to withdrawal criterion 2 and treatment discontinuation criteria 6 and 7 can reasonably be assumed to be missing completely at random (MCAR). It is expected that a limited amount of the missing data will be due to these criteria. For most of the expected missing data, due to the other withdrawal criteria and subjects withdrawing at own will the MAR assumption may be questionable. Therefore, the sensitivity analyses described below will be used to investigate whether the results from the secondary analysis are robust against departures from the assumption of MAR.

Sensitivity analyses

Let δ be defined as the difference between the mean of the observed data and the mean of the unobserved data $\mu_{\text{unobs}} - \mu_{\text{obs}}$, adjusted for other observed data. Under an MAR analysis, δ is assumed to be 0. Positive values of δ indicate that subjects with missing endpoint values have smaller reductions from baseline than subjects with observed endpoint values. If subjects primarily withdraw due to perceived lack of efficacy then this could be the most likely direction of departure from MAR though change in truncal fat percentage may not be a parameter that is linked in a simple way to the perceived efficacy level of the individual subject. Let f_1 and f_0 be the fractions of subjects with unobserved endpoint data in the NNC0195-0092 and placebo arms, respectively. The sensitivity analysis is done by adding a quantity Δ to the treatment effect estimate under the MAR assumption (i.e. treatment effect estimate from the secondary analysis of the primary endpoint), where $\Delta = f_1\delta$ if data depart from MAR in the NNC0195-0092 arm only, $\Delta = -f_0\delta$ if data depart from MAR in the placebo arm only, and $\Delta = (f_1 - f_0)\delta$ if data depart from MAR in the same way in both arms. The calculations will use a range of δ values going from 0 to 2% and the approximation that the standard error of the treatment difference is unaffected by the sensitivity analysis²⁹. All subjects from the FAS can be viewed as included in this analysis as subjects with missing endpoint data will be contributing to one of the fraction values f_1 and f_0 . A similar sensitivity analysis will be made for the secondary comparison between NNC0195-0092 and Norditropin[®] FlexPro[®].

Other exploratory analysis of the primary endpoint

Using the same model as were used for the primary analysis of the primary endpoint, additional exploratory analysis will be done by including treatment by sex, treatment by region and treatment by GHD onset type interaction terms, one at a time, to the model. For region, sub group analysis will also be done based on the primary analysis model.

17.4 Secondary endpoints

17.4.1 Supportive secondary endpoints

17.4.1.1 Efficacy endpoints

Changes from baseline to end of main trial period (Week 34) in the following variables will be used to address the primary objective:

- Truncal fat mass
- Truncal lean body mass
- Total fat mass
- Visceral adipose tissue
- Android fat mass
- Gynoid fat mass
- appendicular skeletal muscle mass (ASMM)
- Lean body mass
- Bone mineral content (extension part only)
- Bone mineral density (extension part only)
- IGF-I SDS
- IGFBP-3 SDS
- Scores of the following PRO questionnaires:
 - TRIM-AGHD
 - SF-36v2
- Lipid profile (total cholesterol, HDL- cholesterol, LDL-cholesterol and triglycerides)
- Cardiovascular parameters (hsCRP and IL-6)
- Body weight
- Waist circumference

Changes in total fat mass, truncal fat mass, visceral adipose tissue, android and gynoid fat mass, appendicular skeletal muscle mass, lean body mass, truncal lean body mass, waist circumference and lipids (total cholesterol, HDL- cholesterol, LDL-cholesterol and triglycerides) from baseline to Week 34 will be analysed using an ANCOVA model with treatment, GHD onset type, sex, region,

DM and sex by region by DM interaction as factors and baseline value as a covariate. The lipids data will be log transformed before analysis, both baseline and Week 34 values. From the model the treatment differences (for lipids the treatment differences will be reported as ratios) at Week 34 between NNC0195-0092 and placebo and between NNC0195-0092 and Norditropin[®] FlexPro[®] will be estimated and the corresponding 95% CIs and p-values will be calculated for each endpoint based on the same multiple imputation technique as was used in the primary analysis of the primary endpoint.

Changes in IGF-I SDS and IGFBP-3 SDS from baseline to the 1, 3, 5, 7, 9, 16, 25, 33 and 35 week's measurements will be analysed using a mixed model for repeated measurements (MMRM), with treatment, GHD onset type, sex, region, DM and sex by region by DM interaction as factors and baseline value as a covariate, all nested within week as a factor. An unstructured covariance matrix will be used to describe the variability for the repeated measurements for a subject. From the MMRM the treatment differences at Week 34 between NNC0195-0092 and placebo and between NNC0195-0092 and Norditropin[®] FlexPro[®] will be estimated and the corresponding 95% CIs and p-values will be calculated for each endpoint. Subjects without post-randomisation data for the analysed endpoint will not be included in the analysis.

Changes in scores of TRIM-AGHD (total and individual domain scores), SF-36 (physical and health component summary scores and individual domain scores) from baseline to the 8, 25, and 34 week's measurements will be analysed using a mixed model for repeated measurements (MMRM), with treatment, GHD onset type, sex, region, DM and sex by region by DM interaction as factors and baseline value as a covariate, all nested within week as a factor. An unstructured covariance matrix will be used to describe the variability for the repeated measurements for a subject. From the MMRM the treatment differences at Week 34 between NNC0195-0092 and placebo and between NNC0195-0092 and Norditropin[®] FlexPro[®] will be estimated and the corresponding 95% CIs and p-values will be calculated for each endpoint. Subjects without post-randomisation data for the analysed endpoint will not be included in the analysis.

Changes in cardiovascular parameters (hsCRP and IL-6) from baseline to the 8, 16, 25, and 34 week's measurements will be analysed using a MMRM, with treatment, GHD onset type, sex, region, DM and sex by region by DM interaction as factors and baseline value as a covariate, all nested within week as a factor. An unstructured covariance matrix will be used to describe the variability for the repeated measurements for a subject. The data will be log transformed before analysis, both baseline value and values assessed at post-randomization visits. From the MMRM the treatment differences (ratios) at Week 34 between NNC0195-0092 and placebo and between NNC0195-0092 and Norditropin[®] FlexPro[®] will be estimated and the corresponding 95% CIs and p-values will be calculated for each endpoint. Subjects without post-randomisation data for the analysed endpoint will not be included in the analysis.

- Scores of PRO questionnaire TSQM at Week 34

The scores of PRO questionnaire TSQM at Week 34 will be used to address the primary objective.

The TSQM scores (effectiveness, convenience and global satisfaction scores) at 8, 25, and 34 week's measurements will be analysed using a mixed model for repeated measurements (MMRM), with treatment, GHD onset type, sex, region, DM and sex by region by DM interaction as factors, all nested within week as a factor. An unstructured covariance matrix will be used to describe the variability for the repeated measurements for a subject. From the MMRM the treatment differences at Week 34 between NNC0195-0092 and placebo and between NNC0195-0092 and Norditropin[®] FlexPro[®] will be estimated and the corresponding 95% CIs and p-values will be calculated for each endpoint. Subjects without post-randomisation data for the analysed endpoint will not be included in the analysis.

Changes from baseline to end of extension period (Week 87) in all of the above mentioned variables in [17.3](#) and [17.4.1](#) (not TSQM) as well as bone mineral content (BMC) and bone mineral density (BMD) will be used to support the secondary objective regarding evaluation of efficacy during the extension period. For TSQM the analogous endpoints to support this secondary objective will be scores assessed at Week 87.

The data will be analysed using descriptive statistics. This analysis will be supplemented with exploratory analysis on changes from baseline to end of extension period (Week 87) data based on MMRM analysis models similar to the main trial period data analysis, where NNC0195-0092/NNC0195-0092 and Norditropin[®] FlexPro[®]/Norditropin[®] FlexPro[®] arms will be compared. For TSQM scores the analysis will be made on Week 87 data and not change from baseline data. The interpretation of these analysis results should take into account the added complications inherent in analysing data from an extension period, including selection bias.

The NNC0195-0092 and hGH serum concentration data will be analysed using descriptive statistics. The data will also be used in the population PK analysis described in section [17.6](#).

Compliance with treatment will be evaluated based on time stamps from the ecaps in the extension period and diary data in the main trial period and the extension period. The data will be analysed using descriptive statistics.

A Kaplan-Meier plot of the time-to-withdrawal will be presented by treatment arm and the implication on the efficacy analysis of any marked differences will be commented upon in the clinical trial report.

17.4.1.2 Safety endpoints

The following endpoints will be used to support the secondary objectives of evaluation of safety in both the main (up to week 35) and extension (up to week 88) trial periods:

- Incidence of adverse events, including injection site reactions
- Incidence of clinical technical complaints
- Occurrence of anti-NNC0195-0092 antibodies
- Changes from baseline in physical examination, ECG results and vital signs
- Changes from baseline in clinical laboratory test results including haematology, biochemistry, fasting glucose, fasting insulin, steady state beta cell function (%B) and insulin resistance (IR) (HOMA estimates), and HbA1c levels

Adverse events will be analysed using descriptive statistics. All adverse events with onset after the first administration of trial product and up until Week 34 will be included in the main trial period analysis. The adverse events will be summarised by treatment, MedDRA (Medical Dictionary for Regulatory Activities) system organ class and MedDRA preferred term. The descriptive statistics will include the number and percentage of subjects who experienced adverse events and the number of events. Adverse events will be listed by treatment and subject with information on severity, relationship to trial product and demographics. Adverse events with onset before first dosing will be reported in a separate listing.

All other safety endpoints will be analysed using descriptive statistics. Additionally, an exact logistic regression analysis on the event of experiencing at least one injection site reaction during the main trial period will be done with treatment, GHD onset type, sex, region, DM and sex by region by DM interaction as factors included in the model as factors and number of injections taken in the main trial period included as offset.

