3.1.5 Risks and benefits

The non-clinical safety programme of NNC0195-0092 reveals no special hazards for humans based on conventional studies of safety pharmacology, repeat-dose toxicity or genotoxicity. Non-clinical data is summarised in section [3.1.3](#).

Currently available data on clinical safety and efficacy of NNC0195-0092 is summarised in section [3.1.4](#). The safety profile of NNC0195-0092 has been evaluated in healthy adult subjects receiving single or multiple doses of the drug (NN8640-3915). Overall, the drug was well tolerated. All adverse events were mild, or moderate and primarily observed at the highest dose levels. Most common adverse events were: headache, peripheral oedema, joint pain, muscle pain, transient increase in blood sugar and insulin levels. In a recent trial in patients with adults with GHD (NN8640-3947) receiving multiple doses of the drug, the same safety profile of adverse events were registered. Overall, the safety profile of NNC0195-0092 observed so far is similar to the existing growth hormone products for daily administration e.g. Norditropin®.

Additional details on the trial product are described in the Investigator's Brochure (IB)¹⁷.

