8.5.6 Fasting plasma glucose, fasting insulin, and HbA1c

Fasting plasma glucose, fasting insulin, and HbA1c tests will be assessed at screening and every 2 to 3 months throughout the trial (see section [2](#)). Subjects must be fasting 8 hours before sample collection, with only water allowed. If the subject comes to a fasting visit in a non-fasting state this needs to be recorded in the eCRF.

Rescue criterion for subjects diagnosed with diabetes mellitus before inclusion into the trial: If the HbA1c increases clinically significantly during the trial, the investigator should consider adjusting the anti-diabetic medication according to local practice.

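### Cheap improvement: section 17.4.1.2 prespecifies no between-arm estimate or 95% CI for change in fasting glucose, fasting insulin, HOMA and HbA1c, and an existing model could supply one

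*Protocol*

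**What the plan says.** Protocol section 17.4.1.2 includes among the safety endpoints changes from baseline in clinical laboratory results, with "fasting glucose, fasting insulin, steady state beta cell function (%B) and insulin resistance (IR) (HOMA estimates), and HbA1c levels" named explicitly. Adverse events are summarised descriptively by treatment. For the rest, "All other safety endpoints will be analysed using descriptive statistics". The one safety model is "an exact logistic regression analysis on the event of experiencing at least one injection site reaction during the main trial period".

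Nothing supplied later alters this for glycaemia. Amendment 1 only takes urinalysis out of the section's endpoint list, apart from its general change to the model factors in section 17. The global amendment to protocol version 2.0 (its section 2.1.36) only moves the adverse-event cut-off from Week 34 to Week 35. SAP version 2.0 adds a TRIM-AGHD sensitivity analysis and a body-weight MMRM.

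Three other places bear on the point:

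- Section 3.1.5 lists "transient increase in blood sugar and insulin levels" among the most common adverse events in healthy subjects and says that the same profile was seen in adults with GHD.
- Section 8.5.6 schedules the glycaemic tests at screening and every 2 to 3 months. If HbA1c rises to a clinically significant degree in a subject with pre-existing diabetes, "the investigator should consider adjusting the anti-diabetic medication according to local practice". The same section states: "If the subject comes to a fasting visit in a non-fasting state this needs to be recorded in the eCRF".
- Section 17.4.1.1 states: "Changes in cardiovascular parameters (hsCRP and IL-6) from baseline to the 8, 16, 25, and 34 week's measurements will be analysed using a MMRM". That model includes treatment, GHD onset type, sex, region, diabetic status, their interaction and baseline, and gives contrasts with placebo and with Norditropin with 95% CIs.

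**The concern.** Section 5.1 describes a trial that compares safety, as well as efficacy, with placebo and with daily Norditropin. Amendment 1 (section 1.1) admitted subjects with diabetes, at the FDA's request, to learn how the drug acts in them, and diabetic status became a stratification factor. Placebo subjects switch to NNC0195-0092 after the main period (section 5.3.6), so the randomised placebo comparison of glycaemia is available only up to then.

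For these endpoints the plan nevertheless promises only summaries. It fixes no contrast, no adjustment and no interval in advance. A reader of the report who wants the size of the glycaemic effect and its uncertainty must build them from the tables, without the precision that baseline and strata could add. Any model chosen after unblinding would be post hoc.

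Two features make raw summaries harder to read. Antidiabetic treatment may be adjusted during the trial, which can lower the mean in whichever arm has more hyperglycaemia. Non-fasting attendance is recorded, but the analysis text does not say what happens to those values.

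**Working it through.** **Inputs.** Completers: 104 NNC0195-0092, 52 placebo, 104 Norditropin (section 17.1). Two-sided 5% level (section 17). Primary-endpoint difference 2.5 and SD 4.5 (section 17.1). The documents give no SD for any glycaemic endpoint.

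**The plan's own figures first.**

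- Power against placebo: SE = 4.5 × sqrt(1/104 + 1/52) = 4.5 × 0.1698 = 0.764, so the noncentrality is 2.5/0.764 = 3.27. Noncentral t with 154 df gives power 0.902. The protocol states 90% and the SAP output 0.902.
- Probability that the half-width against Norditropin is at most 1.3, with 104 per arm: 0.879. The protocol states 0.87 and the SAP output 0.877 and 0.879.
- Drop-out: 260/0.93 = 279.6, rounded up to 280, as stated.

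The design inputs reproduce, so they can be reused for a glycaemic contrast.

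**Precision of an added contrast, in units of the SD of the analysed change.** Half-width = t(0.975, df) × sqrt(1/n1 + 1/n2).

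- Against placebo, 104 v 52: 1.975 × 0.1698 = 0.336 SD.
- Against Norditropin, 104 v 104: 1.97 × 0.1387 = 0.273 SD.

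Adjustment multiplies the half-width by about sqrt(1 − r²), where r is the correlation of baseline with the analysed variable. The documents give no r. Against placebo:

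| Assumed r | Half-width (SD) |
|---|---|
| 0 | 0.336 |
| 0.5 | 0.29 |
| 0.7 | 0.24 |
| 0.8 | 0.20 |

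**Illustration for HbA1c, with assumed SDs of change.** The last column is Phi(0.2/SE − 1.96), with SE = SD × 0.1698. The true rise of 0.2 points is also an assumption.

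| Assumed SD (points) | Half-width v placebo | Half-width v Norditropin | Chance that the CI v placebo excludes zero |
|---|---|---|---|
| 0.3 | 0.10 | 0.08 | 98% |
| 0.4 | 0.13 | 0.11 | 84% |
| 0.5 | 0.17 | 0.14 | 65% |

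These rows use no covariate adjustment. They show that the planned sample supports a useful interval, so leaving it out is a choice of analysis and not a limit of the sample size. They do not show that any planned conclusion is wrong.

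**The case against.** The case for leaving the plan alone is substantial.

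- **Descriptive safety analysis is common practice.** It is applied here to all laboratory safety endpoints alike, and the objective is to evaluate safety, not to test it. This stands: the plan contains no error or contradiction.
- **A reader might infer that the trial never estimates the glycaemic effect, or that neither an effect nor its absence could be concluded.** The documents do not support that. Arm-level n, mean and SD of change, if tabulated, would allow a crude difference and CI; the half-widths above need only n and SD.
- **A reader might see an inconsistency with hsCRP and IL-6.** There is none. Sections 4.3.1 and 17.4.1.1 declare those two as efficacy endpoints, so they receive the efficacy model. They matter here only because a suitable model is already written.
- **A reader might worry that a few diabetic subjects could unbalance the small placebo arm.** Randomisation is stratified by diabetic status (sections 5.1 and 11), which limits exactly this.
- **The model does not remove medication effects.** If treatment changes lower an arm's mean, they lower the MMRM estimate too. This stands, and is why a tabulation is needed beside the model.
- **The non-fasting rule is mainly missing detail.** The eCRF flag makes exclusion possible, and section 17.2 requires exclusions to be documented before database lock. HbA1c is not affected.
- **Part of the risk is covered elsewhere.** A laboratory abnormality needing active management is an adverse event (section 12.1), and adverse events are tabulated by treatment. Section 3.1.5 calls the events in healthy subjects mild or moderate and seen mainly at the highest doses. The diabetic signs in rats occurred in males at 9 mg/kg/day, and the 26-week study showed none (section 3.1.3).

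What survives is narrow: no adjusted contrast with an interval is fixed in advance, for a risk that the protocol names and has the data to quantify.

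**Conclusion.** The point holds as a cheap improvement. Section 17.4.1.2 prespecifies no between-arm estimate, adjustment or CI for the glycaemic endpoints, and neither the amendments supplied nor the SAP adds one. The same subjects would give a 95% CI half-width of about 0.34 SD against placebo and 0.27 SD against Norditropin before adjustment. HbA1c figures in points, and the gain from baseline adjustment, rest on assumed SDs and correlations.

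The primary analysis and the superiority claim are unaffected. Nor would the overall contrast settle how the drug acts in subjects with diabetes, whose number the documents do not give.

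One limit: the full protocol text supplied is version 2.0 with amendments, whereas the SAP refers to version 6.0. The conclusion rests on the text supplied.

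**What to change.** Keep the descriptive tables in section 17.4.1.2 and add to the SAP:

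1. The MMRM structure of section 17.4.1.1 for change in fasting glucose and HbA1c, and on the log scale for fasting insulin, HOMA-IR and HOMA-%B, using the visits at which each is sampled.
2. NNC0195-0092 v placebo and v Norditropin at Week 34, as differences (ratios for the log-scale endpoints) with 95% CIs, labelled as estimates with no confirmatory claim.
3. A table by arm of subjects who start or intensify antidiabetic medication. Section 8.3.3 already collects dose, indication and dates. State beside it that the model does not remove this effect.
4. A rule that values flagged as non-fasting are left out of the glucose, insulin and HOMA analyses.

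The cost is SAP wording, five runs of an existing model structure and one table. It needs no new data and no change in sample size. The downside is a few more intervals without multiplicity adjustment, which the labelling in item 2 addresses.
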